If the first 3 evaluable subjects in a cohort complete Cycle 1 of therapy with no DLT, dose escalation to the next cohort may proceed. If 1 of the first 3 evaluable subjects in a cohort experiences a DLT, enrollment will proceed until there are at least 6 evaluable subjects in that cohort. If no additional subject experiences a DLT, dose escalation may proceed. If 2 or more subjects experience a DLT in a cohort (whether in the initial 3-subject cohort or following expansion to 6 subjects), dose escalation will not occur and the recommended Phase 2 dose (RP2D) will be determined according to the instructions that follow.

Each subsequent cohort will be opened upon completion of the previous cohort. A safety review meeting will be held prior to each dose escalation.

The provisional RP2D will be defined as the dose level at which pharmacodynamic effects are observed in the absence of clinically relevant toxic effects (that is, measurable pharmacodynamic effects with no DLT in the first 3 subjects or ≤ 1 DLT in the first 6 subjects enrolled at that dose level). After discussion with the Investigator, the Sponsor may choose to enroll additional subjects at the RP2D.

A DLT is defined as any IMC-CS4-related adverse event (AE) that occurs during Cycle 1 and does not improve to Grade ≤ 2 (unless stated otherwise), despite medical management, including steroids (if applicable) within 7 days of documented occurrence. The following are considered DLTs:

- Grade 4 neutropenia lasting ≥ 7 days;
- Grade 3 or 4 neutropenia complicated by fever $\geq 38.0^{\circ}\text{C}$ or infection;
- Grade 4 thrombocytopenia;
- Grade 3 thrombocytopenia complicated by hemorrhage;
- Grade 3 or 4 anemia;

- Grade 3 or 4 nonhematologic toxicity. Exceptions maybe be made for the following, if agreed upon by the Sponsor AND the Investigator:
 - Grade ≥ 3 liver function test (LFT) abnormality, such as alkaline phosphatase, gamma glutamyl transferase (GGT), aspartate aminotransferase (AST), and alanine aminotransferase (ALT), without evidence of hepatic injury
 - Transient Grade ≥ 2 bilirubin elevation in the presence of known liver metastases lasting ≤ 7 days
 - Laboratory abnormalities that are reversible to Grade ≤ 2 or baseline levels within 7 days after initial documentation or that are deemed not clinically significant
 - Grade 3 elevation of CK **WITHOUT** elevation in serum and urine myoglobin is **NOT** considered a DLT.

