4 INVESTIGATIONAL PLAN

4.1 Overall Study Design and Plan

This open-label, dose-escalation, Phase 1 study will enroll a total of approximately 72 subjects to 2 parts - Parts A and B, in approximately 6 study sites in the United States. Part A consists of dose escalation of IMC-CS4 using weight-based dosing (Part A enrollment is planned to be discontinued as of 30 September 2015); Part B will consist of dose escalation of IMC-CS4 using non-weight-based dosing; the actual enrollment will depend on the number of DLTs observed and the resultant size of each cohort. Throughout this protocol, any information not indicated as “Part A only” or “Part B only” is relevant to both parts. In Part A, additional subjects were enrolled to the maximum tolerated dose (MTD) of 1.25 mg/kg q2w, in order to help establish the safety profile of IMC-CS4. In Part B, the cohort associated with the dose identified as the MTD may be expanded (up to a maximum of 12 evaluable subjects) in order to help establish the safety profile of IMC-CS4. Enrollment to the MTD expansion cohort may cease if the Sponsor (after conferring with the investigators) deems the toxicity profile precludes further enrollment. Refer also to Section [4.1.2](#).

Dose cohorts, including dose and dosing schedule, are summarized in [Table 1](#). For each cohort, one cycle is 6 weeks. In each cohort, subjects will receive IMC-CS4 by I.V. infusion (with an observation period, in Part A only, for weekly [qw] and every-2-week [q2w] cohorts, in Cycle 1 only, as described in [Table 1](#)). Beginning with Protocol Amendment Version 7.0, enrollment to Part B of the study will start with Cohort 6a, then escalate to Cohorts 7a and 8a. In the event 2 or more subjects on Cohort 6a experience a DLT event, concurrent enrollment of 3 to 6 subjects to each of Cohorts 6b and 6c will start and further dose escalation (that is, to Cohort 7a) will cease. Likewise, the same algorithm will apply for Cohorts 7a and 8a if enrollment to those cohorts occurs. Subjects will be assigned to “b” and “c” cohorts by the Sponsor. Note that there will be no Cycle 1 observation period for Part B cohorts. No intra-subject dose-escalation is permitted for any subject. Dose escalation may be reduced or ceased at any time based on safety and PK behavior.

Table 1. Dose Cohort Assignment

Cohort	Dose Level	Dosing Schedule^a	Cycle 1 Observation Period^b	Number of Infusions
Part A (weight-based dosing)				

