4.1.1 Cohort Enrollment and Dose Escalation

Each cohort will initially enroll at least 3 subjects. In the first cohort (Cohort 1), subjects were to be enrolled sequentially. That is, there was to be a minimum of a 7-day waiting period between the time a subject receives the first dose of IMC-CS4 and when the next subject in Cohort 1 receives his or her first dose.

For all subsequent cohorts, no 7-day waiting period is required.

Beginning with Cohort 2 and provided safety is acceptable, concomitant enrollment of subjects at different sites will be permitted, in order to ensure that at least 3 subjects will be treated for at least 1 cycle. In a case where consent is obtained simultaneously for 2 subjects at 2 different sites, this may result in enrollment of 4 subjects rather than 3 in a cohort; however, no more than 4 subjects should be enrolled in a cohort before safety data from Cycle 1 are available for review.

For all cohorts, all subjects who complete the first treatment cycle (that is, receive all scheduled treatments for Cycle 1 and complete the observation period, as needed) or discontinue therapy due to a DLT will be considered evaluable subjects and will be included in the DLT analyses. Subjects who do not complete Cycle 1 for reasons other than a DLT will be replaced for the analysis until the cohort includes 3 evaluable subjects (or 6 evaluable subjects in case of one DLT in the first 3 subjects); however, if benefitting from treatment (that is, no disease progression or other withdrawal criteria), any subject in Cohort 3 and beyond who experiences a DLT may continue to receive IMC-CS4 upon agreement of the Sponsor and according to the dose reduction guidelines for this study. Refer to Section 10.1 for details of general dose modifications for IMC-CS4.

If the first 3 subjects in a cohort complete Cycle 1 of therapy with no DLT (defined in Section 4.1.4), dose escalation to the next cohort may proceed. If one of the first 3 subjects in a cohort experiences a DLT, enrollment will proceed until there are at least 6 evaluable subjects in that cohort. If no additional subject experiences a DLT, dose escalation may proceed. If 2 or more subjects experience a DLT in a cohort (whether in the initial 3-subject cohort or following expansion to 6 subjects), dose escalation will not occur and the RP2D will be determined according to the instructions in Section 4.1.2.

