In all cases, dose escalation will occur only if the criteria described in this section (Section 4.1.1) are met. Each subsequent cohort will be opened upon completion of the previous cohort. A safety review meeting will be held prior to each dose escalation.

4.1.2 Determination of the Recommended Dose for Phase 2

The provisional RP2D will be defined as the dose level at which pharmacodynamic effects are observed in the absence of clinically relevant toxic effects (that is, measurable pharmacodynamic effects with no DLT in the first 3 subjects or ≤ 1 DLT in the first 6 subjects enrolled at that dose level). After discussion with the Investigator, the Sponsor may choose to enroll additional subjects at or below the RP2D.

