4.4 Continued Access Period

All subjects remaining on study treatment without disease progression or unacceptable toxicity following the final analysis for RP2D will be able to enter the continued access period of the study. The continued access period begins after study completion and ends at the end of trial. During the continued access period, subjects on study treatment who continue to experience clinical benefit may continue to receive study treatment until disease progression, death, unacceptable toxicity, or start of new anticancer treatment. The continued access period includes a Follow-up visit. The Follow-up visit begins 1 day after the subject and the Investigator agree that the subject will no longer continue treatment in the continued access period and lasts approximately 30 days. If it is deemed to be in the best interest of the subject to start a new anticancer treatment prior to the scheduled end of the Follow-up visit, the Follow-up visit duration may be shortened. In this case, the follow-up assessments should be completed prior to the initiation of the new therapy.

Subjects must sign a new ICF before entering the continued access period. The Sponsor will notify investigators when the continued access period begins.

During the continued access period, all AEs, SAEs, study drug dosing, and dose reduction of treatment will be collected on the eCRF.

Serious adverse events will also be reported to Lilly Global Patient Safety and collected in the Lilly Safety System. In the event that an SAE occurs, additional information (such as local laboratory results, concomitant medications, and hospitalizations) may be requested by the Sponsor in order to evaluate the reported SAE.

Investigators may perform other standard procedures and tests needed to treat and evaluate subjects; however, the Sponsor will not routinely collect the results of these assessments.

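### Section 4.1.2 lets 0 DLTs in the first 3 subjects meet the provisional RP2D criterion whatever happens in later subjects at that dose, and no numeric DLT limit applies to subjects 7 to 12

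*Protocol*

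**What the plan says.** **RP2D criterion.** Protocol 4.1.2 calls the RP2D provisional and asks for pharmacodynamic activity without clinically relevant toxicity. A parenthesis then spells that out: "measurable pharmacodynamic effects with no DLT in the first 3 subjects or" at most 1 DLT in the first 6 enrolled at that dose level. The Synopsis repeats it ("effects with no DLT in the first 3 subjects or" the same second limb). Section 4.1.2 also lets the Sponsor add subjects at or below the RP2D.

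**Escalation rule.** Under 4.1.1, a cohort goes to 6 evaluable subjects after 1 DLT in the first 3. If 2 or more have a DLT, "whether in the initial 3-subject cohort or following expansion to 6 subjects", then "dose escalation will not occur and the RP2D will be determined according to the instructions in Section 4.1.2".

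**Part B cohorts.** Under 4.1, once 2 or more subjects in 6a have a DLT, "concurrent enrollment of 3 to 6 subjects to each of Cohorts 6b and 6c will start and further dose escalation" ceases. Cohorts 7a and 8a follow the same pattern.

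**Expansion.** Also in 4.1, the Part B cohort at the MTD "may be expanded (up to a maximum of 12 evaluable subjects", and enrollment may stop if the Sponsor, having consulted the investigators, "deems the toxicity profile precludes further enrollment".

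**Review and analysis.** Section 12.8 requires a meeting when 2 subjects in one cohort have DLTs, and at least quarterly. Section 12.2 and SAP 5.1.3 assign RP2D determination to the DLT population. SAP 5.3.4.4 counts subjects with DLTs. Section 4.4 refers to subjects still on treatment "following the final analysis for RP2D" but gives no criterion for that analysis.

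**The concern.** The two limbs of 4.1.2 are the conditions under which 4.1.1 permits escalation: 0/3, or 1/3 followed by no further DLT. They work as a dose-selection rule only if enrollment at the dose stops when the limb is met. Here it need not stop. The b and c cohorts may hold 3 to 6 subjects, subjects may be added at the RP2D, and the MTD cohort may go to 12. Once 0/3 has been seen, the first limb stays satisfied however many later subjects have DLTs.

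After 6a has been stopped for DLTs, the main decision left for 6b and 6c is which of them, if either, is the RP2D. Defining the non-weight-based RP2D is a Part B secondary objective (2.2). A dose with 2/6 or 3/6 could be named without departing from the written criterion. An outcome in which no dose qualifies is also harder to declare.

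**Working it through.** **The plan's own figures.** Section 12.1 gives about 72 subjects: 30 in Part A plus 9 to 42 in Part B. These reproduce: 30 + 42 = 72, and 3 cohorts × 3 = 9. The minimum of 9 shows that cohorts may end at 3 subjects. No target or assumed DLT rate is stated, so the rate p below is an assumption, shown from 20 to 50%. Subjects are taken as independent.

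**The pattern.** With q = 1 − p, for a cohort taken to 6:

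- P(0/3) = q³
- P(2 or 3 DLTs in the next 3) = 3p²q + p³
- P(pattern) = q³ × (3p²q + p³)

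**Chance of meeting the criterion.**

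- As written: q³ + 3pq⁵ (0/3, or 1/3 and then 0/3)
- At most 1 of all 6: q⁶ + 6pq⁵

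| p | P(0/3) | P(2 or 3 of next 3) | P(pattern) | Met as written | At most 1 of 6 |
|---|---|---|---|---|---|
| 0.20 | 0.512 | 0.104 | 0.053 | 0.709 | 0.655 |
| 0.30 | 0.343 | 0.216 | 0.074 | 0.494 | 0.420 |
| 0.40 | 0.216 | 0.352 | 0.076 | 0.309 | 0.233 |
| 0.50 | 0.125 | 0.500 | 0.0625 | 0.172 | 0.109 |

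Example at p = 0.30: 0.343 × 0.216 = 0.074. As written, 0.343 + 0.9 × 0.16807 = 0.494. At most 1 of 6, 0.118 + 1.8 × 0.16807 = 0.420. The difference, 0.074, is the pattern itself. Outside this range the pattern has probability 2.0% at p = 0.10 and 4.1% at p = 0.60.

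If both a b and a c cohort go to 6, independently and with the same p, the chance that at least one shows the pattern is 1 − (1 − x)², where x is P(pattern): 10%, 14%, 15% and 12%.

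**What 0/3 establishes.** The one-sided 95% Clopper-Pearson upper limit on the DLT rate is 63% after 0/3, 58% after 1/6, 73% after 2/6 and 85% after 3/6.

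**Expansion to 12.** Suppose the dose enters expansion with at most 1 DLT in 6. The chance of ending with 4 or more in 12 (one third or more) is [P(0/6) × P(≥4 of next 6) + P(1/6) × P(≥3 of next 6)] / P(≤1/6). At p = 0.30 this is (0.118 × 0.070 + 0.303 × 0.256) / 0.420 = 0.204. At p = 0.20, 0.40 and 0.50 it is 0.066, 0.400 and 0.612. Going straight from 0/3 to 12 would give 0.086, 0.270, 0.517 and 0.746 at the four rates, but that is a less natural route. In neither case does a number say when the dose stops qualifying.

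**The case against.** The strongest defence is that the limbs are meant to match cohort size: 3 treated with no DLT, or 6 treated with at most 1. On the literal reading, 0/6, and 1/6 that began 0/3, already fall under the first limb, so much of the second is redundant. That is a fair guess at the intent. But the text joins the limbs as alternatives and offers them as the meaning of its toxicity condition, so that condition is not a separate test.

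Several stronger readings are tempting, and the documents do not support them:

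- *That 4.1.1 declares the cohort failed.* It only bars escalation, which has already ceased for b and c cohorts, and passes the decision to 4.1.2.
- *That 4.1.1 itself leads from 0/3 to 6.* It expands only after 1/3. The allowance for a fourth subject cannot produce the pattern either, since 0/3 plus one subject gives at most 1 DLT. The open routes are the 3-to-6 cohort size and the optional later enrollment.
- *That three subjects settle the RP2D.* The RP2D is provisional, and 12.2 and SAP 5.1.3 use the whole DLT population. That stands, but they name a population and no threshold, and nothing says how provisional becomes final.
- *That nothing covers DLTs in the expansion.* The Sponsor may stop it, and 12.8 requires review at 2 DLTs in a cohort and a judgement on whether DLTs exceed expectation. What is missing is a number. The expansion is also tied to the MTD, which the protocol does not explicitly define, and not to a provisional RP2D based on 0/3.

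A careful team would probably reject 2/6 or 3/6. The criterion should then say so.

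**Conclusion.** The criterion in 4.1.2 and the Synopsis gives the wrong answer when followed literally. A dose at 2/6 or 3/6 that began 0/3 still meets it, and no numeric limit applies to subjects 7 to 12. For a cohort taken to 6, the pattern has probability 5.3%, 7.4%, 7.6% and 6.25% at assumed DLT rates of 20, 30, 40 and 50%. These figures are conditional on enrollment going beyond 0/3 at that dose, and they are not the chance that a poor dose reaches Phase 2: discretion and the 12.8 review come in between. The size is modest, but the correction is one sentence and bears on a secondary objective of Part B.

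**What to change.** In 4.1.2 and the matching Synopsis sentence, state that the DLT part of the criterion applies to every DLT-evaluable subject treated at that dose level and schedule:

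- 3 evaluable: no DLT
- 6 evaluable: at most 1
- 7 to 9 evaluable: at most 2
- 10 to 12 evaluable: at most 3

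A dose that exceeds its limit is no longer the RP2D, pending the 12.8 review. Each limit keeps the observed rate below one third: 2/7 = 29% and 3/10 = 30% are the highest allowed, while 2/6, 3/9 and 4/12 are excluded. The same principle gives at most 1 of 4 or 5, should a cohort be judged at that size.

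**Cost.** Text only. No subjects are added, and the Part B range of 9 to 42 stands. The price is a somewhat lower chance of accepting a tolerable dose: for one cohort taken to 6 at a 20% DLT rate, 70.9% falls to 65.5%. Requiring 6 evaluable subjects in every b and c cohort would give firmer data, but it is a separate trade-off and not part of this change.

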4.1.3 Continuation of Therapy

Planned duration of therapy is not fixed. After one cycle, subjects who are benefitting from treatment may continue to receive IMC-CS4 at the same dose and schedule until there is unequivocal evidence of disease progression or other withdrawal criteria are met. Radiographically confirmed disease progression (that is, numerical progression, per RECIST) only is not sufficient to discontinue treatment (refer to Note in Section 4.1). Permitted dose modifications are described in Section 10.1. Subjects who do not meet any withdrawal criteria are eligible to continue receiving study therapy in a subsequent cycle even if one or more doses have been missed during the prior cycle.

4.1.4 Dose-Limiting Toxicity Definition

A DLT is defined as any IMC-CS4-related AE that occurs during Cycle 1 and does not improve to Grade ≤ 2 (unless stated otherwise), despite medical management, including steroids (if applicable) within 7 days of documented occurrence. The following are considered DLTs :

- Grade 4 neutropenia lasting ≥ 7 days;
- Grade 3 or 4 neutropenia complicated by fever $\geq 38.0^{\circ}\text{C}$ or infection;
- Grade 4 thrombocytopenia;
- Grade 3 thrombocytopenia complicated by hemorrhage;
- Grade 3 or 4 anemia;
- Grade 3 or 4 nonhematologic toxicity. Exceptions maybe be made for the following, if agreed upon by the Sponsor AND the Investigator:
 - Grade ≥ 3 liver function test (LFT) abnormality, such as alkaline phosphatase, gamma glutamyl transferase (GGT), aspartate aminotransferase (AST), and alanine aminotransferase (ALT), without evidence of hepatic injury
 - Transient Grade ≥ 2 bilirubin elevation in the presence of known liver metastases lasting ≤ 7 days
 - Laboratory abnormalities that are reversible to Grade ≤ 2 or baseline levels within 7 days after initial documentation or that are deemed not clinically significant
 - Grade 3 elevation of CK WITHOUT elevation in serum and urine myoglobin is NOT considered a DLT.

If benefitting from treatment (that is, no disease progression or other withdrawal criteria), any subject in Cohort 3 and beyond who experiences a DLT may continue to receive IMC-CS4 upon agreement of the Sponsor and according to the dose reduction guidelines for this study (Section 10.1).

4.2 Study Duration

All subjects should continue to receive treatment until there is unequivocal evidence of progressive disease (PD) (radiographically confirmed disease progression [that is, numerical disease progression, per RECIST, Section 11] only is not sufficient to discontinue treatment [refer to Note in Section 4.1]), toxicity requiring cessation, protocol noncompliance (in the opinion of the Investigator or Sponsor), withdrawal of consent by the subject, or until other withdrawal criteria are met (see Section 10.2).

4.3 Study Completion and End of Trial

The study will be considered complete (that is, the scientific evaluation will be complete [study completion]) after the last subject has completed the DLT assessment period (that is, has received all scheduled treatments for Cycle 1 and completed the observation period, as needed) OR has discontinued therapy due to a DLT.

IMC-CS4 may be made available after completion of the study to subjects who are still receiving and benefitting from study treatment.

“End of trial” refers to the date of the last visit or last scheduled procedure for the last subject.

4.4 Continued Access Period

All subjects remaining on study treatment without disease progression or unacceptable toxicity following the final analysis for RP2D will be able to enter the continued access period of the study. The continued access period begins after study completion and ends at the end of trial. During the continued access period, subjects on study treatment who continue to experience clinical benefit may continue to receive study treatment until disease progression, death, unacceptable toxicity, or start of new anticancer treatment. The continued access period includes a Follow-up visit. The Follow-up visit begins 1 day after the subject and the Investigator agree that the subject will no longer continue treatment in the continued access period and lasts approximately 30 days. If it is deemed to be in the best interest of the subject to start a new anticancer treatment prior to the scheduled end of the Follow-up visit, the Follow-up visit duration may be shortened. In this case, the follow-up assessments should be completed prior to the initiation of the new therapy.

Subjects must sign a new ICF before entering the continued access period. The Sponsor will notify investigators when the continued access period begins.

During the continued access period, all AEs, SAEs, study drug dosing, and dose reduction of treatment will be collected on the eCRF.

Serious adverse events will also be reported to Lilly Global Patient Safety and collected in the Lilly Safety System. In the event that an SAE occurs, additional information (such as local laboratory results, concomitant medications, and hospitalizations) may be requested by the Sponsor in order to evaluate the reported SAE.

Investigators may perform other standard procedures and tests needed to treat and evaluate subjects; however, the Sponsor will not routinely collect the results of these assessments.

4.5 Discontinuation of Study Sites and Discontinuation of the Study

Individual study site participation may be discontinued if the Sponsor, the Investigator, the IRB/aEC, or the regulatory authority deems it necessary for any scientific, medical, or ethical reason.

The study will be discontinued if the IRB/aEC or the Sponsor, while considering the rights, safety, and well-being of the subject(s), judges it necessary for any scientific, medical, safety, regulatory, ethical, or other reasons consistent with applicable laws, regulations, and Good Clinical Practice (GCP).

